Putative mechanisms of action for the COMBINATION NB is especially relevant for reducing binge eating and weight per hypothesized effects on brain regions implicated in the regulation of food intake and weight based on the mechanisms of action of leptin (Billes & Greenway, 2011). Leptin's anorectic effects result from its excitatory effects on pro-opiomelanocortin (POMC) neurons in hypothalamus melanocortin system (Crowley et al, 2001; Marsh et al, 1999). Stimulated POMC signaling decreases food intake, increases energy expenditure, but is then inhibited by endogenous feedback (Crowley et al., 2001). Thus, combining these two drugs is to stimulate POMC neurons (bupropion) plus block endogenous feedback that inhibits POMC activity (naltrexone) (Greenway et al., 2009; Biles & Greenway, 2013). This synergistic model received support both in vitro and in vivo studies (Greenway et al., 2009; Cone et al., 2001). Billes and Greenway (2013) noted that NB was associated with ability to control food intake and reduced food craving and, in turn, weight loss.

4. **Research Plan:** Summarize the study design and research procedures using non-technical language that can be readily understood by someone outside the discipline. **Be sure to distinguish between standard of care vs. research procedures when applicable, and include any flowcharts of visits specifying their individual times and lengths.** Describe the setting in which the research will take place.

Pre-Randomization	Stage 1	Stage 2	Follow-Up

 
• Response to Recruitment
 
• Pre-Screening
 
• Baseline Assessment
 
	
 
• Initial Randomization
 
• Participation in Stage 1
 
• Stage 1 Post Assessment Classification as Responder or Non-Responder
 
	
 
• Response-based Randomization
 
• Participation in Stage 2
 
• Stage 2 Post Assessment
 
	
 
• 6-Month Follow-Up Assessment
 
• 12-Month Follow-Up Assessment
 

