**LDX Pharmacotherapy Treatment Protocol.** Medication will be double-blind; patients and study staff, physicians and investigators will be blind to medication assignment. **LDX, FDA-approved for BED**, will be prescribed per procedures found to be superior to placebo in two large-scale phase 3 RCTs (McElroy et al., 2015). The LDX (dose-optimization at 50-70mg per day) protocol followed the McElroy et al (2015) RCT findings that 50-70mg/day dosing was significantly superior to 30mg/dosing and to placebo.

During week 1, LDX will be 30 mg/day for initial titration. During week 2, LDX will be titrated to 50mg/day. During weeks 3-4, LDX increases to 70mg will be made based on acceptable tolerability and clinical need. If 70mg is not tolerated, downward titration to 50mg/day can occur. For the remaining treatment (weeks 4-12), the optimized LDX dose (50 or 70 mg/day) will be maintained.

For the Stage 2 randomized maintenance (double-blind) treatment, a similar approach to dose-optimization will be followed for responders. "Responders" re-randomized to LDX will continue taking LDX at the same dose as Stage 1. "Responders" randomized to placebo will be switched from LDX to placebo. Participants will be instructed to take the medication (active or placebo) once daily in the morning.

Safety and tolerability will be assessed during study clinic visits as will clinical compliance with the study medication. During the dose-optimization period, if the patient develops tolerability concerns, dosing can be reduced once to achieve tolerability. If the patient cannot tolerate the medication, has adverse effects, or is non-compliant with medication for > 7 consecutive days, s/he will be discontinued from the medication arm. Physician visits will be brief (10-15 minutes) and focus on compliance with dosing and evaluating side effects without integrating dietary, behavioral, or CBT techniques.

In Stage 1 or Stage 2, participants taking medication for greater than 4 weeks, a taper will be provided (Refer to Minimizing Risk section on page 20 for details).

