**(5) Secondary Aim:** Generate estimates of cost-effectiveness. We will compute within-study costs for CBT, LDX, CBT+LDX and SMART Stage 2 interventions. Repeated assessments will track additional clinician visits and medication use in our RCT as well as outside treatment contacts through the 18-months. SF-12, administered pre- and post-treatments and at follow-ups, will be used to calculate quality-adjusted life years (QALY) following established methods (Revicki et al., 2005) also used in BED studies of cost-effectiveness specifically of LDX (Agh et al., 2016) and CBTgsh (Lynch et al., 2010; Dickerson et al., 2011), as well as for obesity (Tsai et al., 2005; Malone et al., 2005) including obesity medications (Ara et al., 2012), and for similar SMART designs (switching medication for initial non-responders) in depression (Singh et al 2017). We will calculate incremental cost-effectiveness ratios (ICERs) for the various arms; in these ICERs, the numerator will be the incremental medical cost and the denominator will be the incremental effectiveness of the specific treatment compared to CBT. Confidence intervals for the ICERs will be determined using non-parametric bootstrapping. These ICERs will be compared to the two previous BED (Agh et al., 2016; Lynch et al., 2010) analyses and inform subsequent more definitive larger-scale effectiveness studies.

**POWER ANALYSIS:** We calculated our sample size to have at least 80% power at 2-tailed alpha level 0.025 (adjust for 2 outcomes) to detect clinically meaningful effects in Stage 1 for co-primary outcomes (binge eating and weight loss) and Stage 2 for primary outcome (relapse by initial Responders) at 2-tailed level of 0.05 according based on documented effects of the two treatment components (LDX and CBT). In Stage 1, with 180 subjects total (60 per treatment group), accounting for up to 20% dropout, we can detect medium effect sizes ( $d=0.64$ ,  $f=0.32$ ) for the between group comparisons with more than 80% power at two-sided alpha level of 0.025. These effect sizes are smaller than the effect sizes calculated based on data (Telch et al., 1990; [name] et al., 2005; McElroy et al., 2015, McElroy 2016) which ranged  $d=0.69$  to  $d=0.78$  for the comparison of CBT to LDX on binge-eating and was  $d=1.53$  for LDX vs CBT on percent weight loss. Dropout

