rate estimated based on completion rates for [name] RCTs with BED: 87% in [name] & Masheb, 2005; 84% in [name], White et al., 2014; and previous grant 2R01 DK49587-15 testing stepped care multi-modal treatment and obesity medication along with the LDX RCTs (McElroy et al., 2015, 2016). For binary outcomes (remission), we can detect the following clinically meaningful differences in proportions (63% vs 35%, 66% vs 38%) at 2-tailed alpha of 0.025 in Stage 1. These are in line with observed proportions for CBT (62% by Wilson et al (2010); 64% by Striegel-Moore et al. (2010); LDX (40% and 36% by McElroy et al (2015; 2016) in BED subjects uncomplicated by co-morbidity. Thus, we are well powered for realistic and meaningful effect sizes for both primary and secondary outcome variables. In Stage 2, we expect to randomize 65-70% of subjects as Responders (per McElroy et al 2017); thus we anticipate to have about 80 subjects from the LDX and CBT+LDX groups for the comparisons of interest. Assuming further 20% dropout, we will have 64 subjects with complete data at the end of Stage 2. With this sample size, we have 89% power at two-sided alpha level of 0.05 to detect differences in relapse reported by Hudson et al (2015) of 4% vs 32% (LDX vs placebo). We would have over 80% power to detect differences for the following rates between placebo and LDX: 10% vs 39%, 15% vs 46%, 25% vs 58%.

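### Does the Stage 2 relapse power count forget the 20% Stage 1 dropout?

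*Combined protocol and SAP*

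**What the plan says.** All of this is in the Power Analysis paragraph of Section I, item 13 (Statistical Considerations), unless another place is named.

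- **Stage 1.** The plan states that "with 180 subjects total (60 per treatment group), accounting for up to 20% dropout, we can detect medium effect sizes", namely d = 0.64 at two-sided 0.025.
- **Entry to Stage 2.** "In Stage 2, we expect to randomize 65-70% of subjects as Responders", citing a published time-course paper; "thus we anticipate to have about 80 subjects from the LDX and CBT+LDX groups for the comparisons of interest".
- **Stage 2 loss.** "Assuming further 20% dropout, we will have 64 subjects with complete data at the end of Stage 2".
- **Power for relapse (two-sided 0.05).** 89% for 4% vs 32%. Then: "We would have over 80% power to detect differences for the following rates between placebo and LDX", listing 10% vs 39%, 15% vs 46% and 25% vs 58%.
- **Remission (secondary).** "we can detect the following clinically meaningful differences in proportions (63% vs 35%, 66% vs 38%) at 2-tailed alpha of 0.025 in Stage 1". No sample size or power is printed with these pairs.

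The design table in item 4 (Research Plan) places "Stage 1 Post Assessment Classification as Responder or Non-Responder" at the end of Stage 1. The LDX Pharmacotherapy Treatment Protocol says that Responders re-randomised to LDX "will continue taking LDX at the same dose as Stage 1", while the others switch from LDX to placebo.

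**The concern.** Stage 1 power is calculated after taking off up to 20% dropout. The Stage 2 count shows no matching step: two thirds of the full 120 is 80. If 65-70% is a response rate among people who reach the end-of-Stage-1 assessment, it should be applied to 96 rather than 120, and the 64 is too large.

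Relapse is the Stage 2 primary outcome. The three further pairs are the only stated cover if relapse on LDX exceeds 4%, and they sit just above 80% at 32 per arm, so any uncounted loss would take them below it. The dosing text also presumes that Responders are still on LDX when Stage 2 starts, so following up Stage 1 dropouts would not by itself put them into the Stage 2 comparison.

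The remission pairs raise a similar question: they have about 80% power only if all 60 per group are counted.

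**Working it through.** **Inputs.** From the Power Analysis: 60 per Stage 1 arm, so 120 on LDX or CBT+LDX; up to 20% Stage 1 dropout; 65-70% randomised as Responders; a further 20% Stage 2 dropout; completion of 84% and 87% in two cited trials. From Background: the unrounded relapse rates, 3.7% vs 32.1%. From the Responder randomisation section: equal allocation.

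**Formula (unpooled normal, n per arm).** Power = Φ( |p1 − p2| / √[(p1q1 + p2q2)/n] − 1.96 ), with q = 1 − p.

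**1. Reproducing the plan.** 120 × 0.65 = 78 and 120 × 0.70 = 84, hence about 80. Then 80 × 0.8 = 64, or 32 per arm.

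| LDX vs placebo | Difference / SE at n = 32 | Power | Printed |
|---|---|---|---|
| 3.7% vs 32.1% | 0.284 / 0.0890 = 3.19 | 89.1% | 89% |
| 4% vs 32% | 0.280 / 0.0894 = 3.13 | 87.9% | 89% |
| 10% vs 39% | 0.290 / 0.1012 = 2.87 | 81.7% | over 80% |
| 15% vs 46% | 0.310 / 0.1084 = 2.86 | 81.6% | over 80% |
| 25% vs 58% | 0.330 / 0.1161 = 2.84 | 81.1% | over 80% |

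The printed figures are recovered, the 89% with the unrounded rates. Of the methods tried, only this one meets them all. For the three pairs at 32 per arm, the pooled formula gives 78.3%, 78.2% and 77.7%, and exact chi-squared gives 80.6%, 79.6% and 79.7%.

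**2. Share applied to Stage 1 completers, 20% dropout in both stages.** 120 × 0.8 = 96 assessed; 96 × 0.65 to 0.70 = 62-67 Responders; × 0.8 = 50-54 with complete data, or 25-27 per arm.

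| Pair | Power at 25 per arm | Power at 27 per arm |
|---|---|---|
| 3.7% vs 32.1% | 80.5% | 83.4% |
| 4% vs 32% | 79.0% | 82.0% |
| 10% vs 39% | 71.6% | 74.9% |
| 15% vs 46% | 71.5% | 74.8% |
| 25% vs 58% | 71.0% | 74.3% |

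**3. Same reading with the cited completion rates in both stages.** 120 × 0.84 × 0.65 × 0.84 = 55.0, up to 120 × 0.87 × 0.70 × 0.87 = 63.6. That is 27-32 per arm, and 74-82% for the three pairs.

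**4. Same reading, all 62-67 randomised Responders analysed (31-33 per arm).** About 80-83% for the three pairs.

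**5. What the literal reading implies.** If 78-84 of the 120 enter Stage 2 as Responders and Stage 1 dropout is at its 20% ceiling, response among those assessed is 78/96 = 81% to 84/96 = 88%, leaving 12-18 assessed non-responders. At 84-87% completion (101-104 assessed), it is 78/104.4 = 75% to 84/100.8 = 83%, leaving 17-26.

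**6. Remission, two-sided 0.025.** The unpooled formula, with 2.241 in place of 1.96, gives 83% for both pairs at 60 per group and 73% at 48. The pooled formula gives 81% at 60 and 70% at 48.

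**The case for a change.** The strongest case for a change is that the printed power for a primary outcome cannot be checked without knowing what 65-70% is a percentage of. On the completer reading at 20% dropout, the three pairs fall below 80% under the pooled, arcsine and exact chi-squared methods as well as the unpooled one. The literal reading has its own cost: at the dropout ceiling it needs 81-88% response among those assessed, and it leaves few people for naltrexone/bupropion vs placebo. The plan states neither consequence.

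This stands as a remark on clarity. The denominator is not written down, and the cited source cannot be consulted here to settle it. As a charge of error it does not stand, for four reasons.

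- The percentage is attached to being randomised in Stage 2, and the next loss is called a further one. That wording fits a share already net of Stage 1 loss.
- The 20% is a ceiling, and the plan cites 84-87% completion. At those rates even the completer reading gives a range that reaches the printed claim.
- The comparison in non-responders is described as exploratory and carries no power claim, so a small group there contradicts nothing.
- The remission pairs have about 80% power at 60 per group, in keeping with the intent-to-treat analysis, and no printed figure is contradicted.

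Replacing the three pairs with wider ones would not clearly help. Pairs chosen for 80% power with the unpooled formula at 25 per arm (10% vs 43%, 15% vs 50%, 25% vs 62%) can still miss it under the planned chi-squared test: exact power is 79.0% for 15% vs 50% at 25 per arm, and 78.3-78.6% for 25% vs 62% at 26-27 per arm.

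**Conclusion.** No change follows. Taken as written, about 80 of 120 enter Stage 2 and 64 complete it, and the stated powers reproduce with the unpooled normal formula. The lower figure of 71-75% for the three illustrative pairs needs two things the plan does not state: that 65-70% is a rate among Stage 1 completers, and that dropout reaches its 20% ceiling in both stages. With the cited completion rates the same reading gives 74-82%. Even at the ceiling, the documented relapse difference on which Stage 2 was sized keeps about 79-83%, depending on whether the rates are rounded.

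These figures rest on the unpooled formula. The pooled one runs about 3 to 5 points lower, and it does not reproduce the plan's own claims at 32 per arm.

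What remains is an unstated denominator in a planning paragraph. Supplying it would leave enrolment, randomisation, the relapse analysis and the conclusions drawn from it as they are.

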**Randomization to Stage 2 Treatments for LDX and CBT+LDX (Stage 1) “Responders”.**

“Responders” to Stage 1 LDX (i.e., LDX and CBT+LDX) treatments will be defined as 65% or greater reduction in binge-eating. This cut-point is based on reliable findings regarding prognostic significance of such reductions ([name] et al., 2006; 2012) and supported by recent report on “time course of the effects of LDX” (McElroy et al., 2017). “Responders” will be randomized in equal proportions (using stratified blocked randomization with Stage 1 treatment as a stratifying variable) to LDX or placebo (double-blind) for 12 weeks.

**CBT Treatment Protocol.** CBT will be delivered by trained and monitored research clinicians following manualized protocols we have used successfully in previous RCTs (e.g., [name] et al., 2005, [name] et al., 2011). CBT will be delivered in individual sessions weekly for 12 weeks following CBT manuals based on Fairburn et al (1993) used in our RCTs ([name] et al., 2005, 2011) which are similar to those used in major RCTs testing CBT delivered via 12-24 weeks (Wilfley et al., 2002; Wilson et al., 2010). The CBT manuals provide detailing session-by-session procedures for clinicians and parallel guides are provided to the patients to facilitate homework and mastery of the material. CBT, a specialist focal treatment, consists of

three overlapping phases. Phase one involves establishing a collaborative therapeutic relationship while focusing on educating the patient about the nature of binge-eating and factors thought to maintain the problem. Specific behavioral strategies (e.g., self-monitoring) are used to help patients identify problematic eating patterns while establishing a normal structured eating pattern. Phase two integrates cognitive restructuring procedures, where patients learn to identify and challenge maladaptive cognitions regarding eating and weight/shape and thoughts that trigger binge-eating. Phase three focuses on maintenance of change and relapse prevention.

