#### **Assessment of Treatment Outcome and Time Course.**

Primary Measures: (1) Binge-eating frequency (EDE); (2) weight (measured weight and height and BMI); for Stage 2 LDX vs Placebo test: "Relapse" to DSM-5 threshold of once-weekly binge eating on EDE

Secondary Measures: (1) "remission" (zero binges past 28 days on EDE; eating disorder pathology (EDE global), depression (BDI-II); for exploration of mediators: (2) eating behaviors (EDE, TFEQ, FCI-II), executive control and impulsivity (BIS-11, DDT, Trails) and selected metabolic measures (lipid profiles, HbA1c, blood pressure, HR) to characterize metabolic outcomes and allow comparison with RCTs for LDX and NB.

**Figure 2.** Grid depicting when each measurement is obtained

Assessment Points	BASELINE (2 MTG)	DURING RX STAGE 1 1-MONTH	DURING RX STAGE 1 2-MONTH	POST RX STAGE 1 3-MONTH	DURING RX STAGE 2 4-MONTH	DURING RX STAGE 2 5-MONTH	POST RX STAGE 2 6-MONTH	6 AND 12- MO FOLLOW- UP (18 MONTH TOTAL)
MINI Psychiatric Interview, Height, Credibility,	•							
EDE Interview, SF-12, GPAQ, Lipid Profile, HbA1C, Glucose	•			•			•	•
EDE-Q-I, BDI-II, GLTEQ, Weight, BP, HR	•	•	•	•	•	•	•	•
TFEQ-Restraint	•	•		•			•	•
DDT	•	•		•			•	
FCI-II, PFS	•	•		•	•		•	
BIS-11	•	•		•	•		•	•
ELOCS	•	•		•				
Trails, YFAS, BRS, Amphetamine Testing	•			•			•	
Placebo Ratings					•		•	
Start of New Treatments				•			•	•
Medical History Creatinine w/ EGFR PSQI	•			•				
Adverse Events		•	•	•	•	•	•	
Insulin	•			•				

Liver Function	•			•	• (Non- responde rs only)			
Pregnancy Test	•			•				

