### DATA ANALYSIS

Baseline demographic and clinical characteristics for randomized groups will be compared using chi-square tests for categorical variables, and ANOVA or Kruskal-Wallis tests for continuous variables. Continuous variables will be examined for adherence to normal distribution using normal probability plots and Kolmogorov-Smirnov tests. If normality not satisfied and transformations do not help with achieving normality, alternative analytic strategies will be considered such as generalized estimating equations or nonparametric methods. Dropouts and completers will be compared. Analyses will be intent-to-treat; patients will be followed regardless of treatment completion to minimize missing data. Primary outcomes will be tested at two-sided 0.05 significance level. Secondary analyses will be adjusted for multiple tests using Bonferroni correction.

Overall Data Analysis Strategy will involve MIXED EFFECTS MODELS (Diggle et al, 2002, Gueorguieva & Krystal, 2004) to compare treatments. These models allow for different numbers of observations per subject, use all available data on each subject, and are unaffected by randomly missing data. Further advantage is capacity to test and account for individual-difference contributions to treatment outcomes (Cudeck, 1996; Cudeck & Klebe, 2002; Hedeker et al., 1996; Hedeker & Gibbons, 1996; Singer, 1998). They provide flexibility in modeling the correlation structure of data. In models for each outcome, we will include fixed effects of time, treatment, and interaction between time and treatment, and random subject-level effects. Because we cannot a priori predict the shape of responses over time in each arm of the trial we will first treat time as a categorical predictor and will then test for polynomial trends over time. We will consider different error structures (e.g., AR1, independence) and select the best fitting one based on information criteria. We will

compare dropout patterns between groups and if there are concerns of informative dropout or informative intermittent missing data, we will use pattern mixture models (Hedeker & Gibbons, 1997) to perform sensitivity analyses.

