analytic strategy of studies testing medication for maintenance (i.e., fluoxetine) for bulimia nervosa (Romano et al (2002) and for anorexia nervosa (Walsh et al (2006) which was recently used in the Shire maintenance study of LDX for BED (Hudson et al., 2015). Stage 2 LDX and placebo will be compared on the proportion of Stage 1 responders who “relapse” using chi-squared tests and Cox Proportion Hazards Tests; we will explore further using survival analyses to estimate whether time to relapse differs between LDX and placebo. For the secondary outcomes, we will use mixed effects models to assess whether there is significant change in binge eating or weight loss between the group who continue LDX treatment and the group who receive placebo. We anticipate that subjects randomized to LDX maintenance will maintain better outcomes than patients randomized to placebo. We will also perform parallel analyses on all three groups (CBT, LDX, CBT+LDX) to compare outcomes at the 6-month time point (i.e., comparing 3-month CBT and 6-month two-stage treatments).

(4a) **STAGE 2 – Secondary Aim 1:** Explore LDX and CBT effects, alone and in combination, for longer-term BED outcomes. Our two-stage design will also allow us to also compare CBT (i.e., Stage 1 CBT-only short-term) versus the Stage 2 LDX/placebo maintenance treatment (i.e., Stage 2 LDX/placebo following Stage 1 LDX or Stage 1 CBT+LDX) for longer-term outcomes through 18 months. This will inform clinical questions regarding whether LDX maintenance treatment following either acute LDX treatment or acute combined CBT+LDX differ and whether it offers any additional benefits over acute CBT-only (4b).

**STAGE 2 – Secondary Aim 2:** Among Non-responders to Stage 1 treatments with LDX, Explore the effectiveness of switching to an alternative medication (NB versus placebo). Primary outcomes will be reducing binge-eating and reducing weight and secondary outcomes will be binge-eating remission, eating-disorder pathology, and depression. We will use similar analyses to Primary Aim 1: mixed models for the continuous outcome variables and logistic regression for categorical (remission) variable.

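### The Stage 2 relapse analysis has no rule for responders without a month-6 EDE, so an observed-only test can lose true relapses

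*Combined protocol and SAP*

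**What the plan says.** All references are to the combined protocol and SAP.

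- **Analysis principle** (Data Analysis, opening paragraph): "Analyses will be intent-to-treat; patients will be followed regardless of treatment completion to minimize missing data". The same section relies on mixed models for incomplete data and adds pattern-mixture models as a sensitivity analysis if dropout looks informative.
- **Stage 2 primary test** (Data Analysis, Stage 2 Primary Aim 1): the proportion of Stage 1 responders who relapse is compared between lisdexamfetamine (LDX) and placebo "using chi-squared tests and Cox Proportion Hazards Tests". Mixed models are assigned to the Stage 2 secondary outcomes.
- **Event** (Assessment of Treatment Outcome and Time Course): relapse is return to the "DSM-5 threshold of once-weekly binge eating on EDE".
- **Timing** (Figure 2): between Stage 2 randomisation and the end of Stage 2, the EDE interview falls at months 3 and 6 only. The self-report EDE-Q-I is also collected at months 4 and 5.
- **Removal** (Withdrawal From Treatment and Other Treatments; Use of Placebo, item d): intensification of binge eating is listed among the grounds for removing a participant from the study.
- **Size** (Power Analysis): "we anticipate to have about 80 subjects from the LDX and CBT+LDX groups", then "Assuming further 20% dropout, we will have 64 subjects with complete data at the end of Stage 2". On that number, "With this sample size, we have 89% power at two-sided alpha level of 0.05" for relapse rates "of 4% vs 32% (LDX vs placebo").

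**The concern.** A chi-squared test needs a yes or no for every person. A Cox model needs an event time or a censoring time. The plan supplies neither for a responder who leaves before the month-6 EDE. Without a rule, standard software omits that person from the chi-squared test. The Cox model helps little as written, because the defining instrument is not scheduled at months 4 or 5, so someone lost before month 6 may contribute no EDE information on relapse.

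This matters more here than for most outcomes. Responders switched to placebo are the group in whom binge eating is expected to return, and its return can lead to removal. The event can therefore cause its own missing value. The Stage 2 primary result is at stake: an observed-only comparison may undercount relapse, and mostly in the arm where relapse is commoner.

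**Working it through.** **Inputs.** About 80 randomised responders, 20% dropout, 64 with complete data, two-sided alpha 0.05 and relapse of 4% vs 32% (all Power Analysis). Allocation is 1:1: responders are "randomized in equal proportions (using stratified blocked randomization with Stage 1 treatment as a stratifying variable"). Per arm this is 80/2 = 40 randomised and 64/2 = 32 complete. Splits of missing patients between arms, and relapse rates among them, are my assumptions.

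**1. Reproduce the plan's power.** 80 × 0.8 = 64.
- Exact power: add P(x)·P(y) over all tables with uncorrected Pearson p ≤ 0.05, where x ~ Bin(32, 0.04) and y ~ Bin(32, 0.32). Result: 89.25%.
- Arcsine formula: Φ(|2·asin√0.32 − 2·asin√0.04|·√(32/2) − 1.96) = Φ(0.800 × 4 − 1.96) = Φ(1.24) = 89.2%.

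The stated 89% reproduces. With all 80 observed at the same rates (40 per arm), exact power is 95.0%. Losing 16 people at random therefore costs about 6 points.

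**2. Which tool covers which outcome.**

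| Stage 2 outcome | Test | Missing-data handling stated |
|---|---|---|
| Relapse (primary) | Chi-squared, Cox | None |
| Binge frequency, weight (secondary) | Mixed models | Likelihood-based; pattern-mixture if needed |

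**3. Loss that depends on relapse.** Suppose the true rates are 4% and 32%, half of relapsers have no month-6 EDE, and everyone else is observed.
- LDX: 40 × 0.04 = 1.6 relapsers, 0.8 seen; 0.8/(40 − 0.8) = 0.8/39.2 = 2.0%.
- Placebo: 40 × 0.32 = 12.8 relapsers, 6.4 seen; 6.4/(40 − 6.4) = 6.4/33.6 = 19.0%.

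The difference shrinks from 28 to 17 percentage points. Exact power with 39 and 34 observed is 72%. Only 0.8 + 6.4 = 7.2 people are lost, fewer than half of the 16 allowed for, yet the cost is 95 − 72 = 23 points.

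**4. One data set, same mechanism.** Suppose true relapse is 2/40 vs 13/40, p = 0.0016. If the 8 missing on placebo all relapsed and the 8 missing on LDX did not, the observed-only test sees 2/32 vs 5/32, p = 0.23.

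**5. The opposite direction.** Suppose observed relapse is 1/32 vs 10/32, p = 0.003, with 8 missing per arm.

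| Relapses among the missing (LDX, placebo) | Table | Pearson p |
|---|---|---|
| 0, 0 | 1/40 vs 10/40 | 0.0035 |
| 8, 8 | 9/40 vs 18/40 | 0.033 |
| 3, 0 | 4/40 vs 10/40 | 0.0775 |
| 8, 0 | 9/40 vs 10/40 | 0.79 |

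Of the 9 × 9 = 81 possible splits, 28 give p > 0.05. In every one of those, more of the missing LDX patients than of the missing placebo patients have relapsed.

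**6. Effect of the scoring rule on power.** Assume 20% missing in each arm and 4% vs 32% among those observed.
- All missing counted as relapsed: 0.04 × 0.8 + 0.2 = 23.2% vs 0.32 × 0.8 + 0.2 = 45.6%; exact power 56%.
- All missing counted as not relapsed: 0.04 × 0.8 = 3.2% vs 0.32 × 0.8 = 25.6%; exact power 88.6%.

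**The case against.** The best defence is that the 64 is an ordinary dropout allowance in a sample-size calculation and not an analysis set. That is right. A reader might infer that the relapse test is planned on 64 completers and that 16 people are deliberately left out. The documents do not say so: the Stage 2 section refers to Stage 1 responders without restriction, and the intent-to-treat sentence stands. A reader might also infer from step 6 that true power is 56%. That figure follows only from scoring every dropout as relapsed. Some will leave for intolerance or non-compliance, which are not relapse.

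Stopping treatment is also not the same as missing the month-6 EDE. Patients are to be followed regardless of treatment completion, the post-Stage 2 assessment is paid, and dropouts are invited back for follow-up evaluations (Payments for Participation). The number missing may be below 16. It may also be higher: the monitoring plan cites 20% to 38% attrition in earlier drug studies in this disorder, and 38% of 80 is about 30.

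Third, the Cox model can use partial follow-up through censoring. That holds in principle, but the plan gives no censoring rule and schedules no EDE between months 3 and 6.

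Finally, an observed result of the planned size is not fragile under every rule. Scoring the missing the same way in both arms, all relapsed or none, keeps it significant (p = 0.033 or 0.0035).

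These points remove the stronger readings. They do not supply the missing rule.

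**Conclusion.** The concern holds as an unspecified rule on a primary outcome. The plan states intent-to-treat but gives no handling of missing relapse status for the chi-squared test, no censoring rule for Cox, and no sensitivity analysis for either. The 89% is correct for 64 complete cases and need not be restated.

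Under the mechanism that the plan itself makes plausible, removal because binge eating has intensified, an observed-only test is biased towards no difference. A reader might infer that the gap flatters LDX. That would require relapse among the missing to be concentrated on LDX, and nothing in the documents points that way. It remains possible and should be shown by sensitivity analysis.

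The size depends on assumptions. If half of relapsers are lost, power is about 72% against 95% with everyone observed. The one-half, the equal 8 and 8 split and the illustrative counts are mine. The 80, the 20% and the 4% vs 32% are the plan's.

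**What to change.** Before Stage 2 is unblinded, add to the Stage 2 Primary Aim 1 analysis:

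1. The analysis set is all randomised responders, in the arm assigned.
2. Anyone removed from the study for intensified binge eating counts as relapsed.
3. For any other responder without a month-6 EDE, relapse status is informed by the month-4 and month-5 EDE-Q-I, either directly at the same once-weekly threshold or through multiple imputation.
4. The same data define Cox event and censoring times.
5. A tipping-point table shows how many missing patients in each arm would have to relapse to change the conclusion. Counting all dropouts as relapsed is one scenario in it and not the primary rule.

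The cost is SAP wording and one extra table, with no new visits, patients or measures. The downside is that the EDE-Q-I is self-report, so the instrument differs from the EDE for these patients. Both instruments are scheduled at months 3 and 6, so their agreement can be estimated in this trial and used in the imputation, and the sensitivity analyses should show what the substitution does. Patients lost before month 4 will have no Stage 2 questionnaire and rest on imputation and the tipping-point table alone.
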